## **Secondary Endpoints:**

1. To compare the reduction/rates of TE events and procedure-related complications (DRT, pericardial effusion/cardiac tamponade, or CVA/TIA) in patients after successful PDL closure with any of the three closure modalities
  - a. Periprocedural complications occurring from Postoperative day #0 – day 7
  - b. Delayed procedure-related complications and adverse events within 90 days of procedure

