## **Data/Variable Points for Collection:**

- Age
- Sex
- Height
- Weight
- BMI
- Diabetes (y/n)
- Smoking (y/n)
- Dyslipidemia (y/n)
- Prior stroke/TIA (y/n)

- Prior deep venous thrombosis/pulmonary embolism (y/n)
- Ejection Fraction
- History of CAD (y/n)
- Congestive heart failure (y/n)
- Chronic Kidney Disease (y/n)
- Type of Atrial Fibrillation (paroxysmal, persistent, permanent)
- Baseline antithrombotic regimen (aspirin, clopidogrel/prasugrel/ticagrelor, warfarin, direct oral anticoagulant, heparin)
- TIA/stroke after Watchman
- History of major bleeding
- High Fall risk (y/n)
- Previous major bleeding (y/n)
- Previous minor bleeding (y/n)
- Thromboembolism while on oral anticoagulant
- CHA2DS2-VASc Score
- HAS-BLED Score
- Time passed since LAA closure (months)
- Type of LAA Closure (watchman/watchman FLX, amulet, lariat, surgical ligation, atriclip)
- Device Size (if applicable)
- Thrombus on device (y/n)
- Peri-device/central leak size in mm
- Acute success (end of procedure closure) (y/n)
- Procedure duration (minutes)
- Flourosopy time (minutes)
- Contrast usage (mL)
- Hospital length of stay
- Type of procedural anesthesia (general vs light sedation vs local)
- Procedural imaging (TEE, ICE, or both)
- Devices attempted
- Devices deployed
- Combination procedures (combined AF ablation, or LAA occlusion + AF ablation)
- Size/number of devices (plugs/coils)
- Major procedural complications from postoperative day 0-7: stroke, TIA, air embolism, myocardial infarction, cardiac tamponade, device embolization, ventricular tachycardia
- Minor procedural complications from postoperative day 0-7: pericardial effusion
- Complications seen within 90 days of the procedure: cardiovascular death, non-cardiovascular death, stroke/TIA, pericarditis
- Follow-up transesophageal echocardiogram time (months)
- Size of leak at follow up (in mm)
- Follow-up time
- Follow up antithrombotic regimen

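### The secondary endpoint and the data collection list do not match on device-related thrombus or on pericardial effusion and tamponade after day 7

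*Combined protocol and SAP*

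**What the plan says.** All sections cited are in the combined protocol and SAP.

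Secondary Endpoints compares thromboembolic events and "procedure-related complications (DRT, pericardial effusion/cardiac tamponade, or CVA/TIA") "in patients after successful PDL closure with any of the three closure modalities". Two sub-items follow. The first covers periprocedural complications from day 0 to day 7. The second is "Delayed procedure-related complications and adverse events within 90 days of procedure". The text does not expand DRT; it is taken here to mean device-related thrombus.

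Data/Variable Points for Collection has three complication items:

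- "Major procedural complications from postoperative day 0-7: stroke, TIA, air embolism, myocardial infarction, cardiac tamponade", followed by two further events that are neither effusion nor thrombus;
- "Minor procedural complications from postoperative day 0-7: pericardial effusion";
- "Complications seen within 90 days of the procedure: cardiovascular death, non-cardiovascular death, stroke/TIA, pericarditis".

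The only thrombus field is "Thrombus on device (y/n"), which carries no time point. It comes directly after "Device Size (if applicable") and directly before the first of two leak-size items. The second leak-size item is explicitly a follow-up measurement. The follow-up echocardiogram has a time in months but no thrombus finding attached to it.

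**The concern.** Comparing safety between the three modalities is part of the stated objective. In a multi-centre retrospective study, the collection list is the only written guide to what each centre abstracts. It is not described as a minimum, and the 90-day item has no open category for other events.

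A complication that is named in the endpoint but has no field in the list leads to one of two outcomes. Either it goes unreported, or the absence of records is read as an absence of events. The thrombus field carries a further risk: centres may fill in an undated yes/no differently, and thrombus seen before leak closure could be counted as a complication of that closure.

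**Working it through.** The plan gives no figure to reproduce on this point, and no power or event-rate calculation applies. The check is a crosswalk: each named complication, in each window of the endpoint, against the fields in the collection list. CVA in the endpoint is taken as the same event as stroke in the list.

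| Complication named in the endpoint | Day 0-7 | Delayed, to day 90 |
|---|---|---|
| DRT | no timed item | no timed item |
| Pericardial effusion | minor complications item | no item after day 7 |
| Cardiac tamponade | major complications item | no item after day 7 |
| CVA/TIA | major complications item | 90-day item |

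1. **Count, with the endpoint's list applied to both windows.** 4 complications × 2 windows = 8 cells. Four have a timed item: effusion, tamponade and stroke/TIA at day 0-7, and stroke/TIA to day 90. The other 8 − 4 = 4 do not: DRT in both windows, and delayed effusion and delayed tamponade.

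2. **Count, if effusion and tamponade were meant as day 0-7 events only.** Two cells drop out, leaving 8 − 2 = 6 required. Four are still covered, and 6 − 4 = 2 are not, both of them DRT. The DRT gap does not depend on how the delayed window is read.

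3. **Could another item stand in?** Pericarditis, in the 90-day item, is a different event from effusion or tamponade. The follow-up echocardiogram time dates a scan but records no thrombus result. No other section supplies the missing fields.

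4. **What the thrombus field can and cannot show.** A single undated yes/no cannot distinguish three histories: thrombus present before leak closure and later resolved, thrombus present before and after, and thrombus new after closure. Leak size has two separately timed items and so does not have this problem.

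5. **What is not affected.** Leak size before closure and at follow-up are both collected, so this point does not touch the primary endpoint. Stroke/TIA has a field in each window, so post-closure rates can be computed.

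No rate per modality is estimated. The documents give no event rates, and the endpoint is confined to patients with successful closure, whose number per modality is not stated.

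**The case against.** The best defence is that the collection list already puts each window into practice. It has a day 0-7 block and a 90-day block, mirroring the two sub-items of the endpoint. On that view effusion and tamponade are periprocedural events, while death, stroke/TIA and pericarditis are the delayed ones. The endpoint never literally names delayed effusion or tamponade. This much stands: applying the parenthetical list to the second window is an inference. It is the natural one, because both windows are sub-items of the sentence that contains the list and the second again refers to procedure-related complications. If the narrower meaning was intended, the endpoint needs to say so.

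A second defence is that a thrombus field does exist and nothing labels it as baseline. That also stands. Its position suggests a pre-procedure item, but the list is loosely ordered (a history of major bleeding appears twice, for instance), so position is weak evidence. A reader might infer that thrombus after closure is simply not collected. The documents do not support that; they support only that the timing is ambiguous. The ambiguity is enough to prevent a clean DRT comparison.

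A reader might also note how much of the 90-day window falls after day 7 and infer that most effusions and tamponades would be missed. The documents do not support that either: a share of calendar time is not a share of events.

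**Conclusion.** The mismatch is real and should be corrected. It affects components of a secondary endpoint: DRT on any reading, and delayed effusion and tamponade on the natural reading. In the crosswalk, four of eight cells lack a timed item, or two of six if effusion and tamponade are confined to day 0-7. These counts describe coverage of the endpoint by the list; the number of events lost cannot be estimated from the documents.

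The conclusion assumes that centres abstract what the list contains and no more. It would be tempting to conclude that the safety comparison as a whole cannot be made. That goes too far, since day 0-7 effusion and tamponade, and stroke/TIA in both windows, are collected.

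**What to change.** **Effusion and tamponade.** Add both to the 90-day item in Data/Variable Points for Collection, as a yes/no within 90 days in the same form as stroke/TIA, with the event day where available. An entry without a day is still usable and should be kept. If these were meant as day 0-7 events only, state that in Secondary Endpoints instead.

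**DRT.** Replace the single thrombus field with two: thrombus before leak closure, and thrombus at follow-up imaging. Each should allow yes, no, not applicable and not reported, with the day of imaging. State whether the field refers to the device from the original LAAC or to the one placed at leak closure, and how RFA and surgical-ligation cases are handled; otherwise DRT is not comparable across modalities. Abstract both fields from existing imaging reports, and do not relabel values already entered. Report DRT as found at follow-up imaging, with the imaging day, and not as a 90-day rate: the imaging required under Exclusion Criteria is at 45 days and cannot establish status to day 90.

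**Fallback.** The Informed Consent section says records were de-identified. If they cannot be re-linked, remove DRT from the comparison in Secondary Endpoints and state that it was not ascertained.

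**Cost.** Extra chart and imaging-report abstraction at each centre, with no new tests and no re-reading of images. Some values will be not reported, because the follow-up imaging was required for leak re-evaluation and reports may not mention thrombus or effusion.
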